5.4.2. Examination of Subgroups

The list of subgroups may be used in descriptive summaries and statistical analyses. Additional subgroups of clinical interest may also be considered.

- If the percentage of subjects is small within a particular subgroup, then the subgroup categories may be refined.
- If the category cannot be refined further, then descriptive rather than statistical comparisons may be performed for the particular subgroup.

Subgroup	Categories
Index exacerbation severity	Moderate vs. Severe
Baseline COPD maintenance therapy type	Possible categories of interest are: Monotherapy vs. Dual therapy vs. Triple therapy
Index exacerbation type	New vs. Relapse
Number of exacerbations in the previous 12 months	Possible categories of interest are: 0 vs. 1 vs. ≥ 2
Gender	Male vs. Female
Smoking status	Current vs. Former
Baseline COPD ICS therapy use	ICS Use vs. Non-ICS Use
Baseline Blood Biomarker Status	
 • For High sensitivity CRP: Bacterial vs. Non-Bacterial • For Procalcitonin: Bacterial vs. Non-Bacterial • For Eosinophils: High vs. Low

5.5. Other Considerations for Data Analyses and Data Handling Conventions

Other considerations for data analyses and data handling conventions are outlined in the appendices:

Section	Component
Section 13.2	Appendix 2: Assessment Windows
Section 13.3	Appendix 3: Study Phases and Treatment Emergent Adverse Events
Section 13.4	Appendix 4: Data Display Standards & Handling Conventions
Section 13.5	Appendix 5: Derived and Transformed Data
Section 13.6	Appendix 6: Reporting Standards for Missing Data
Section 13.7	Appendix 7: Values of Potential Clinical Importance

6. STUDY POPULATION ANALYSES

6.1. Overview of Planned Study Population Analyses

The study population analyses will be based on the “APE” and/or “MITT” populations, unless otherwise specified.

Study population analyses including analyses of participant’s disposition, protocol deviations, demographic and baseline characteristics, and exposure and treatment compliance will be based on GSK Core Data Standards. Details of the planned displays are presented in [Appendix 11: List of Data Displays](#).

6.1.1. Concomitant medications

Concomitant medications will be summarised by treatment group. Separate summaries of Baseline and On-treatment (Step-up) COPD Maintenance Therapy, and duration of OCS use will also be presented.

Additional summaries or sensitivity analyses of on-treatment COPD maintenance therapy (step-up therapy) may be performed if the data indicate that further investigation is warranted.

7. EFFICACY ANALYSES

Details of the outputs are provided in [Appendix 11: List of Data Displays](#) and will be based on GSK data standards and statistical principles.

Further details for use in the endpoint derivations below can be found in [Appendix 5: Derived and Transformed Data](#).

7.1. Primary Efficacy Analyses

7.1.1. Primary Endpoint

The primary endpoint of change from baseline in clinic visit trough FEV₁ at Day 84 measured post-bronchodilator is defined as:

FEV₁ measured prior to dosing and post-bronchodilator on Day 84 – Post-bronchodilator Baseline FEV₁

7.1.2. Primary Statistical Analyses

The primary endpoint will be analysed by fitting a suitable dose response model. The following models will be fitted, and the one that gives the best fit to the data will be selected: Bayesian 4-parameter E_{max} dose response model, 3-parameter E_{max} model and a Log-linear model.

The 4-parameter E_{max} dose response model will take the form:

$$\text{Change from baseline FEV}_1 = (E0 + a_1 * \text{baseline}) + \frac{(E_{\max} + b_1 * \text{baseline}) * \text{Dose}^\gamma}{ED50^\gamma + \text{Dose}^\gamma}$$

The 3-parameter E_{max} dose response model will take the form:

$$\text{Change from baseline FEV}_1 = (E0 + a_1 * \text{baseline}) + \frac{(E_{\max} + b_1 * \text{baseline}) * \text{Dose}}{ED50 + \text{Dose}}$$

Where: E0 = the response at dose = 0 (placebo)

E_{max} = the maximal response

ED50 = the dose that yields 50% of the maximal response

γ = the slope parameter

a₁, b₁, are covariates for explanatory parameters

Initially, normal non-informative priors will be used for the E0, a₁, a₂, and E_{max} parameters with mean 0 and standard deviation 1E6 L. A functional uniform prior will be used for the ED50 and slope parameters ([Bornkamp, 2014](#)), where the prior density for the functional uniform prior is based on all the parameters in the model. An inverse -

gamma prior with shape of 0.001 and scale of 0.001 will be used for the residual variance. However, if a prior distribution appears not to be truly non-informative then alternative prior distributions may be used.

Parameters will be blocked such that the MCMC procedure samples from E_0 , a_1 , b_1 , and E_{\max} , first, then the ED50 and slope parameters and then finally the residual variance parameter. For the functional uniform priors, the density will be calculated for values of dose from 0.0001 to 750 in steps of 50 (i.e. 0.0001, 50.0001, 100.0001, ..., 750.0001). For the continuous covariates, the density will be calculated from the minimum to the maximum in 10 equal steps. For binary covariates the density will be calculated for values 0 and 1. If the model does not converge including covariates, the model may be fitted with covariates removed.

If the log-linear model is fitted an offset of 1 will be used.

The posterior median change from baseline with 95% Highest Posterior Density (HPD) Credible Intervals, will be presented for each dose along with the adjusted median difference from placebo with 95% HPD, calculated at the mean baseline value across the treatment arms. Posterior probabilities that the true improvement is greater than 0 mL and 75 mL will also be presented. Graphical representation of the dose response across the full dose range will also be produced to allow inference to be made for the non-studied doses based upon the model fit.

For the futility analysis:

The predictive probability of success at the end of the study will be calculated (assuming the randomisation ratios remain the same after the interim) for each dose using the formula suggested by [Spiegelhalter, 2004](#) as follows:

$$\text{Predictive probability} = 1 - \Phi \left[\frac{\sqrt{n_1}}{\sqrt{m_1}} z_{0.95} - \sqrt{\frac{n_1 + m_1}{m_1}} \frac{y_n}{\sigma} \right]$$

Where n_1 is the number of subjects with Day 84 data in the active arm of interest, m_1 is the number of subjects yet to be observed in the active arm of interest, y_n is the posterior mean difference from placebo from the fitted model, and σ is the standard deviation of the posterior mean difference from placebo.

For the possible adaptations at Interim Analysis 2:

If the study is not deemed futile, and either the 4 parameter or 3 parameter E_{\max} dose response curves has successfully been fitted to the data then adaptation of the randomisation schedule will be considered, to drop, add or amend doses from the randomisation scheme.

The adaptation will be done by comparing the relative information from alternative randomisation schemes with the original randomisation schemes, such to find the design

that provides the most information about the dose response relationship. The efficiency ratio (ER) for an alternative scheme compared to the original, will be calculated as:

$$ER(\theta_i) = \left(\frac{|M(\xi_1, \theta_i)|}{|M(\xi_F, \theta_i)|} \right)^{\frac{1}{p}}, i=1, \dots, 1000$$

Where $M(\xi, \theta)$ is the information matrix for the design ξ and model parameters $\theta = (e0, emax, ed50, \gamma, a1, b1)^T$, ξ_1 is the alternative design one and ξ_F is the fixed original design, and p is the number of parameters (Dette, 2008). In order to ensure any adaptation is robust to the variability in the parameter estimates at the interim analysis, 1000 samples will be generated from the posterior distribution of the parameters $\theta_1, \dots, \theta_{1000}$ and the ER calculated for each set of parameter. Adaptation will then only take place if the median ER is >1.05 and the 10th percentile of the ER is >1 . The efficiency ratio will be estimated using the mean baseline value across the population.

The alternative designs that will be considered will depend on the dose response model fitted but could include:

1. Add 25mcg dose
2. Add 25mcg dose, drop 500mcg dose
3. Add 25mcg dose, drop 250 mcg and 500 mcg doses
4. Drop 12.5mcg dose
5. Drop 12.5 mcg and 50mcg doses

The potential adaption may also be verified in the moderate and severe subgroups to ensure the adaption is beneficial across both groups.

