5. CONSIDERATIONS FOR DATA ANALYSES AND DATA HANDLING CONVENTIONS

5.1. Study Treatment & Sub-group Display Descriptors

Treatment Group Descriptions			
RandAll NG Randomization System		Data Displays for Reporting	
Code	Description	Description	Order in TLF
A	Placebo	Placebo	1
B	GSK2269557 12.5 mcg	NEMI 12.5 mcg	2
C	GSK2269557 25 mcg*	NEMI 25 mcg	3
D	GSK2269557 50 mcg	NEMI 50 mcg	4
E	GSK2269557 100 mcg	NEMI 100 mcg	5
F	GSK2269557 250 mcg	NEMI 250 mcg	6
G	GSK2269557 500 mcg	NEMI 500 mcg	7
H	GSK2269557 750 mcg	NEMI 750 mcg	8

* The nemiralisib dose of 25 mcg may be added following the results of an un-blinded interim analysis if further characterization of the lower end of the dose response curve is required.

Treatment comparisons will be displayed as follows using the descriptors as specified:

1. NEMI 12.5 mcg vs Placebo
2. NEMI 25 mcg vs Placebo
3. NEMI 50 mcg vs Placebo
4. NEMI 100 mcg vs Placebo
5. NEMI 250 mcg vs Placebo
6. NEMI 500 mcg vs Placebo
7. NEMI 750 mcg vs Placebo

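### The 50 mcg grid for the functional uniform prior leaves no point between 0.0001 and 50 mcg, so in the 4-parameter Emax model steep curves that rise below 50 mcg get almost no prior weight

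*SAP*

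**What the plan says.** SAP section 7.1.2 fits a 4-parameter Emax, a 3-parameter Emax and a log-linear model, and "the one that gives the best fit to the data will be selected". For the Emax models, "A functional uniform prior will be used for the ED50 and slope parameters", and "the prior density for the functional uniform prior is based on all the parameters in the model". The computation is then fixed: "the density will be calculated for values of dose from 0.0001 to 750 in steps of 50", with the points listed as 0.0001, 50.0001, 100.0001 and so on up to 750.0001. The section adds that "if a prior distribution appears not to be truly non-informative then alternative prior distributions may be used", without naming a check or a replacement.

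Section 5.1 lists "GSK2269557 12.5 mcg" as a treatment group. It also provides that "The nemiralisib dose of 25 mcg may be added following the results of an un-blinded interim analysis", to be used "if further characterization of the lower end of the dose response curve is required".

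**The concern.** A functional uniform prior is meant to spread weight evenly over curve shapes. Its density is built from the gradients of the curve over the dose range, and the grid is where those gradients are read. A curve that completes its rise between two neighbouring grid points shows almost no gradient at any point, so its density is close to zero whatever its shape. Here the widest blind spot relative to the doses studied is 0 to 50 mcg. That interval holds the lowest arm and the optional 25 mcg dose.

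At stake are the ED50, the shape of the fitted curve and the effects at low doses. The primary objective is to characterise dose response, and section 7.1.2 also uses the fitted curve for doses that were not studied. The convergence diagnostics in section 7.1.2.1 would not reveal the problem, because the chain can converge perfectly well to a posterior built on this prior.

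**Working it through.** **Inputs from the SAP (7.1.2, 5.1).** The grid is 0.0001 + 50k for k = 0,...,15. This gives 16 points ending at 750.0001, as listed, with none strictly between 0.0001 and 50. The arms are placebo, 12.5, 50, 100, 250, 500 and 750 mcg.

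**Assumed, because the SAP gives no figure.** Slope 0.5-10, ED50 1-750 mcg, no baseline covariate. For the posterior runs: SD 0.2-0.3 L, Emax 75-100 mL, and arms of 300/100×5/300 or 150 each.

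**Formula.** Write f = d^γ/(ED50^γ + d^γ). The gradient is J(d) = (1, f, −Emax·(γ/ED50)·f(1−f), Emax·f(1−f)·ln(d/ED50)). The prior density is taken as √det of the average of J(d)J(d)′ over the grid. Emax cancels when two grids are compared.

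**Why the density collapses.** The factor f(1−f) peaks at 0.25 when d = ED50. At slope 4 and d = 50:
- ED50 25: (50/25)^4 = 16, so f(1−f) = 16/17² = 0.055
- ED50 12.5: (50/12.5)^4 = 256, so f(1−f) = 256/257² = 0.0039

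At 100 mcg and above it is smaller still, and at 0.0001 it is effectively zero. The grid therefore sees three distinct positions: zero, 50 mcg and the plateau. A 4 × 4 determinant needs at least four distinct points to be non-zero. The 3-parameter model needs only three, which is why it is largely spared.

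**Prior density, 1 mcg grid divided by SAP grid (slope 4, 4-parameter model).**

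| ED50 (mcg) | Ratio |
|---|---|
| 25 | about 24 |
| 20 | about 95 |
| 12.5 | about 2,000 |

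A 0.1 mcg grid gives nearly the same densities as the 1 mcg grid. A version using only the ED50 and slope gradients shows the same collapse.

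**Prior probability, SAP grid against 1 mcg grid.**
- 4-parameter, P(ED50<25): 0.009 against about 0.034
- 4-parameter, P(ED50<25, slope ≥3): about 0.0001 against about 0.02. Over all bounds tried, the SAP grid gives about 70 to 310 times less.
- 3-parameter, P(ED50<25): about 0.32 against 0.26, a mild shift the other way

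**Posterior, one noise-free case** (300/100×5/300, SD 0.25 L, Emax 100 mL, true slope 4).

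| True ED50 | Quantity | SAP grid | 1 mcg grid | Truth |
|---|---|---|---|---|
| 20 | Effect at 50 mcg (mL) | 63 | 83 | 98 |
| 20 | Median ED50 (mcg) | 40 | 30 | 20 |
| 20 | Effect at 12.5 mcg (mL) | 8 | 3 | 13 |
| 5 | Effect at 12.5 mcg (mL) | 58 | 82 | 98 |

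**Posterior over simulated data (60 sets per scenario).** For steep truths with ED50 5-30, the SAP grid lowers the median effect at 50 mcg by about 9-27 mL. For a shallow truth (ED50 20, slope 1) it lowers it by about 5-11 mL. Pr(difference>0) changes by at most about 0.05.

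**The case against.** The strongest reply has five parts.

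**The grid is part of the stated prior.** The SAP gives no density formula, only a reference and the remark that all parameters enter. It can be argued that the prior on this grid is simply the prior chosen. It is true that the intention cannot be read from the document. But the SAP labels the prior functional uniform and contemplates replacing any prior that turns out informative. On this grid it is far from even over curve shapes.

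**The SAP has an escape clause.** It allows other priors, so a rescue is possible. With no criterion and no named replacement, however, it would be used only if someone happened to notice, and after unblinded interim looks.

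**Low-dose effects are not always shrunk.** A reader might infer that they are. With true ED50 20 and slope 4, the 12.5 mcg estimate is larger and nearer the truth on the SAP grid. With ED50 5 it is smaller and further from it. This part of the reply stands: the direction at 12.5 mcg depends on the curve.

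**Much of the pull remains after refinement.** On the 1 mcg grid the effect at 50 mcg is still 83 mL against 98. In the ED50 20 case the 95% intervals at 50 mcg overlap heavily (18-104 against 29-122 mL), and both contain the truth. This stands as well. Spreading the prior evenly in dose carries its own pull, and that is a choice of prior, not a grid artefact.

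**The effect is conditional.** With a true ED50 of 100 (slope 1 or 2), the median ED50 is the same on both grids and effects at 12.5-100 mcg differ by at most about 5 mL. The 4-parameter model may not be the one selected.

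**Conclusion.** The point holds for the 4-parameter Emax model. As written, the grid gives steep curves that rise below 50 mcg almost no prior weight. If the true curve is of that kind, ED50 is pulled upward and the estimated effect at 50 mcg falls by roughly 5-27 mL. For scale, section 7.1.2 reports the probability of exceeding 75 mL. The millilitre figures rest on assumed SD, arm sizes, effect and parameter bounds; the prior densities rest on the determinant form and on no covariate being included.

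Three stronger readings are not supported:
- **The whole primary analysis is distorted.** The effect is small in the 3-parameter model (density ratio 0.8-1.7 for ED50 12.5-50), absent in the log-linear model, which has no ED50, and small when the true ED50 is near 100 mcg.
- **The success rule is compromised.** Pr(difference>0), which the 90% criterion in section 3.1.1.1 uses, moves by at most about 0.05.
- **The 25 mcg adaptation is biased.** The efficiency ratio at Interim Analysis 2 uses draws from this posterior, so an effect is possible. No ratio was computed under either grid, so none is shown.

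This is a correction that should be made, because following the plan literally yields a prior far from even over curve shapes.

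**What to change.** In section 7.1.2, evaluate the same density on a fine dose grid, for example 0.0001 to 750 in 1 mcg steps, and leave the rest of the prior unchanged. A 1 mcg step is fine enough, since 0.1 mcg gives nearly the same densities. This removes the grid artefact but not all of the prior's pull on ED50. It costs one number in the SAP and slightly more computing time.

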3. PLANNED ANALYSES

3.1. Interim Analyses

Ongoing data reviews of unblinded safety data, conducted by an Internal Safety Review Committee (iSRC), will be performed throughout the trial. Details will be documented in the iSRC charter.

Interim analyses of the primary endpoint and key secondary endpoints to inform internal decision making will be conducted periodically throughout the trial. The first analysis (Interim Analysis 1) is planned to occur when approximately 170 participants complete 28 days of treatment, where approximately 50 of the 170 participants have an index exacerbation defined as severe. A change that could arise from this interim analysis is a specification of the stratification proportions by index exacerbation severity status (moderate or severe). This decision will be based on inspection of all available endpoints at the interim analysis.

Further interim analyses will be performed, depending on the observed recruitment rate. At least one interim analysis of the primary endpoint of change from baseline in clinic visit trough FEV₁ at Day 84 measured post-bronchodilator will be performed to

determine whether or not any adjustments to the randomization ratio across doses would help optimize the characterization of the dose response profile for nemiralisib. This analysis (Interim Analysis 2) is planned to occur when approximately 300 participants complete 84 days of treatment or when approximately 400 participants remain to be randomized, whichever occurs first. Adjustments could include ceasing randomization to an existing dose(s) of nemiralisib and/or modification of the allocation ratios for the existing nemiralisib doses and/or addition of a 25mcg dose. Other changes may include specification of the stratification proportions by index exacerbation severity status.

An interim analysis of efficacy and safety data collected during the Double-Blind Treatment Period will be conducted when the last participant in the study has completed the 12-week Double-Blind Treatment Period (End of Treatment Interim Analysis). The aim of this analysis is to provide GSK with timely data to inform internal decision making, prior to the end of study.

The following table describes the endpoints that will be analysed/summarised at each interim:

Interim	Purpose of interim	Endpoints

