5.2. Baseline Definitions

For all endpoints, the baseline value will be the latest pre-dose assessment with a non-missing value, including those from unscheduled visits. If time is not collected, Day 1 assessments are assumed to be taken prior to first dose and used as baseline.

Post-bronchodilator Baseline FEV₁ is defined as the latest FEV₁ measured prior to the first dose of study treatment and post-bronchodilator.

Pre-bronchodilator Baseline FEV₁ is defined as the latest FEV₁ measured prior to the first dose of study treatment and pre-bronchodilator.

Baseline CAT Total Score is defined as CAT Total Score measured prior to the first dose of study treatment on Day 1.

Baseline SGRQ Total Score is defined as SGRQ Total Score measured prior to the first dose of study treatment on Day 1.

Unless otherwise stated, if baseline data is missing no derivation will be performed and baseline will be set to missing.

A centred baseline will be derived for each participant by subtracting the mean baseline across all participants from each participant's baseline value. The 'centred' baseline may be used instead of Baseline in the statistical analyses to aid convergence.

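### The efficiency ratio that governs dose adaptation is 0/0 whenever the Emax model carries the baseline terms, because the information matrix is singular at a single baseline value

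*SAP*

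**What the plan says.** Section 7.1.2 defines the Emax mean with baseline entering twice: a1 multiplies baseline in the placebo term and b1 multiplies it in the Emax term.

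For the adaptation at Interim Analysis 2, each alternative randomisation scheme is compared with the planned one through ER = (|M(alternative, θ)| / |M(planned, θ)|)^(1/p). Here M is the information matrix, "\theta = (e0, emax, ed50, \gamma, a1, b1)^T", and "p is the number of parameters". ER is calculated for 1000 posterior draws of θ. The decision rule is "Adaptation will then only take place if the median ER is >1.05 and the 10th percentile of the ER is >1". The covariate is handled in one sentence: "The efficiency ratio will be estimated using the mean baseline value across the population".

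Five candidate schemes are listed, for example "Add 25mcg dose, drop 500mcg dose". Section 5.2 adds that "The 'centred' baseline may be used instead of Baseline in the statistical analyses to aid convergence".

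**The concern.** The plan asks for information on a1 and b1, which describe how response varies with baseline, but evaluates the matrix at one baseline value. No design observed at a single covariate value can separate an intercept from a slope in that covariate. The same holds for Emax and b1. The determinant should then be zero in both numerator and denominator, whichever doses are used.

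ER is the only numerical criterion for changing the randomisation across doses. If it cannot be evaluated as defined, someone must decide what was meant. Section 3.1 lists Clinical Statistics and Clinical Programming among the functions unblinded to interim data, so a repair left until the interim would be chosen by people who can see the results.

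**Working it through.** The SAP reports no ER, so there is no figure to reproduce. The check is whether the definition yields one.

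**Inputs from section 7.1.2.** Mean function μ(d, x) = (E0 + a1·x) + (Emax + b1·x)·h(d), with h(d) = d^γ / (ED50^γ + d^γ); θ with six entries; a single x = x0, the mean baseline.

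**Gradient**, in the order (E0, Emax, ED50, γ, a1, b1):

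f(d, x) = [1, h, (Emax + b1·x)·∂h/∂ED50, (Emax + b1·x)·∂h/∂γ, x, x·h]

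M = Σ over doses of w_d · f(d, x0) f(d, x0)ᵀ, up to the residual variance, which is the same for both designs.

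**Rank.** At x = x0 the a1 entry is x0 times the E0 entry at every dose, and the b1 entry is x0 times the Emax entry. The vectors (−x0, 0, 0, 0, 1, 0) and (0, −x0, 0, 0, 0, 1) are therefore orthogonal to f at every dose and lie in the null space of M. The rank is at most 6 − 2 = 4. For the 3-parameter Emax model, where γ drops out, it is at most 5 − 2 = 3. With the centred baseline x0 = 0, and the a1 and b1 rows and columns are all zero. In each case |M| = 0 for every design.

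**Numerical confirmation.** Assumed values: E0 0.05 L, Emax 0.10 L, ED50 60 mcg, γ 1.2, a1 −0.1, b1 0.03, mean baseline 1.3 L. Two allocations over placebo, 12.5, 50, 100, 250, 500 and 750 mcg were tried: equal, and 3:1:1:1:1:1:3.
- The rank was 4 of 6, and 3 of 5 for the 3-parameter model, for the planned design and all five alternatives, at x0 = 1.3 and at x0 = 0.
- Over 1000 assumed parameter draws the rank was 4 every time (planned design, 4-parameter model).
- Computed 6×6 determinants were exactly 0 or no larger than about 3 × 10⁻⁴⁴ in size, with negative signs: rounding error.
- Rounding error can look like an answer. With equal allocation, adding 25 mcg gave (−1.374 × 10⁻⁴⁴) / (−2.620 × 10⁻⁴⁴) = 0.524, and 0.524^(1/6) ≈ 0.90, a plausible-looking ER with no meaning.

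**What a repair would give (illustration only).** Neither the allocation nor the parameter values are fixed in the SAP text. Single-point values for Emax 80 mL, ED50 50 mcg, γ 1.2, b1 = 0, weights 3:1:1:1:1:1:3, baseline 1.2 L (SD 0.45), with 25 mcg added at weight 1 and the weights rescaled:

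| Alternative | Dose-response block at mean baseline, p = 4 | All six parameters, averaged over baselines, p = 6 |
|---|---|---|
| Add 25 | 1.057 | 1.028 |
| Add 25, drop 500 | 1.093 | 1.049 |
| Add 25, drop 250 and 500 | 1.103 | 1.054 |

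The first two alternatives cross 1.05 between repairs. The third, which ranks highest, exceeds 1.05 under both. With equal allocation and the same parameters, the first two fail under both repairs and the third changes from 1.066 to 1.011.

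The actual rule uses the median and 10th percentile over draws. With 1000 assumed draws around the parameter values of the numerical confirmation, and weights 3:1:1:1:1:1:3, adding 25 and dropping 500 gave:
- p = 4 block: median 1.065, 10th percentile 1.044 (meets the rule);
- same block with p = 6: median 1.043, 10th percentile 1.029 (does not), consistent with 1.065^(4/6) ≈ 1.043;
- six parameters averaged over baselines: median 1.030, 10th percentile 1.016 (does not).

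A wider single-point scan (ED50 10 to 200 mcg, slope 1 to 2, both allocations) asked whether the best of the five alternatives passes 1.05. The two repairs agreed in 22 of 30 settings and differed in 8.

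**The case against.** The algebra is not in dispute. The other side is about reach and consequence.

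- **The intended reading is recoverable.** The stated aim is information about the dose-response relationship, and evaluation at the mean baseline suggests the four-parameter curve there. The oldest superseded SAP text in the same file listed only e0, emax, ed50 and γ. This stands as evidence of intent, and it supports the first repair. But the current text lists six parameters and defines p as their number. The choice between p = 4 and p = 6 alone can change the outcome.
- **ER is not always undefined.** Section 7.1.2 allows covariates to be removed if the model does not converge with them. Then a1 and b1 disappear and ER exists. This stands, so the point is confined to fits that include the baseline terms.
- **A test on dummy data would expose a zero determinant.** Often it would, but rounding can return a finite ratio, as shown above.
- **ER is not the whole decision.** Adaptation also requires that the study is not futile and that an Emax curve has been fitted, and it may be verified in the severity subgroups. This stands; ER is the only numerical criterion, not the only condition.

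A reader might infer that the two repairs lead to opposite decisions. The documents do not support that as a general statement: it depends on an allocation and parameter values that the SAP text does not fix. A reader might also infer that the primary analysis or the futility rule is affected. They are not: ER appears in neither and concerns only how remaining participants are allocated across doses.

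**Conclusion.** The adaptation rule is wrong as written. Whenever the Emax model is fitted with the baseline terms, M has rank 4 of 6 (3 of 5 for the 3-parameter model) at a single baseline value. Both determinants are zero and ER is 0/0 for all 1000 draws. This rests on the SAP's own model, parameter vector and covariate sentence, with no numerical assumption.

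The effect of the repair on the decision is conditional. Under some assumed allocations and parameters, the choice of repair, including p = 4 against p = 6, moves ER across 1.05; under others it does not. That is enough to require the definition to be settled before unblinding, but not to say which way the adaptation would have gone.

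**What to change.** Replace the covariate sentence and the definition of θ in section 7.1.2 with one consistent definition, fixed before unblinding:

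1. Preferred: θ contains only the dose-response parameters (e0, emax, ed50, and γ when fitted), M is evaluated at the mean baseline, and p = 4 (or 3 for the 3-parameter Emax model). This matches the stated aim.
2. Alternative: keep a1 and b1, average M over the observed baseline distribution, and use p = 6 (or 5).

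State p explicitly for each model, and for the fit without covariates. The cost is one sentence in the SAP and a small program change, with no further data.
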